neuroprotection or neuroplasticity. Strømmen et al., (44) recruited 20 acute stroke patients (41.5 ± 14 h post-stroke; mild to no disability) and implemented a 5-day intervention consisting of twice-daily 30-minute bouts of treadmill walking at a moderate exercise intensity (50% of heart rate reserve [HRR]) (45). Standing and sitting rest breaks were permitted as required. More than half of participants experienced at least 1 adverse event (AE) during exercise. Dizziness was the most frequent AE, occurring in 8.5% (19/224) of all exercise sessions, and 4 sessions ended prematurely due to dizziness. In addition, although not reported as an adverse event, 8 sessions were cancelled due to tiredness (5 participants) and 28 sessions finished early due to exhaustion (number of participants not reported). Lastly, the target exercise intensity was only attained in 31% of sessions, and 8 participants (40%) did not achieve the target exercise intensity in any exercise session. The authors attributed the low exercise intensity to lower limb motor deficit which limited step frequency. This suggests that walking may be an unsuitable mode of aerobic exercise training during the acute phase of stroke recovery. No serious adverse events (SAEs) (e.g. neurological deterioration) occurred in the 30-day follow-up period therefore the authors concluded that a 14.7% AE rate was acceptable (33 AEs in 224 exercise sessions). As this was a feasibility trial, clinical outcomes were not explored. The occurrence of dizziness suggests that frequent and prolonged upright standing and walking may induce orthostatic stress which could be detrimental, especially during the acute phase of stroke when blood-brain barrier function is impaired (46). Indeed, standing upright has been shown to reduce CBF velocity by 13% relative to a supine position in chronic stroke (47). The landmark international AVERT trial found that very early (first mobilisation at a median of 18.5 hours post-stroke) and more frequent (3 additional bouts per day) mobilisation (out-of-bed sitting, standing or walking) was associated with a poorer functional outcome at 3 months post-stroke compared to usual care (first mobilisation at a median of 22.4 hours post-stroke). The physiological mechanisms were not explored in the AVERT trial, but it is plausible that orthostatic stress was a contributing factor to the negative outcome (47,48).

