8.3. Safety of aerobic exercise

Low- to moderate-intensity aerobic exercise is considered to be safe for medically stable acute ischaemic stroke patients without contraindications (44,63). The only study which has conducted a moderate-intensity aerobic exercise training intervention (five days of twice-daily, 30-min bouts of moderate-intensity walking exercise) reported no SAEs but occasional dizziness (8.5%; 19/224 sessions) and exhaustion (44). Exhaustion is not classed as an AE but is an important outcome when considering exercise tolerability; 24 out of 224 (10.7%) exercise sessions ended early as a result of exhaustion (9/20 participants). In addition, Kramer et al., (64) investigated the energy cost of two different 6-minute fitness assessments in acute stroke patients (median 4 days post-stroke; mild to moderate stroke; n=21). Ambulatory participants (n=14) performed a 6-minute walk test, whereas non-ambulatory participants (n=7) completed a 6-minute sit-to-stand test. The median rating of perceived exertion (RPE) reported at the end of each test was 12/20 and 13/20 for the walk and sit-to-stand tests, respectively (both moderate intensity). No SAEs or AEs were reported, and only one participant was unable to complete the walk test due to fatigue. Furthermore, Johnson et al., (65) demonstrated the safety of a graded exercise test in acute

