and subacute stroke patients (n=28, days post-stroke: median = 9; range = 5-11), although the authors did not specify the proportion of participants that were in the acute (1-7 days post-stroke) or early subacute phase of stroke (7-30 days post-stroke). One of the exercise test termination criteria was reaching 85% of age-predicted maximum heart rate (HRmax), which is classed as vigorous exercise intensity (45). Over half of the participants exceeded this upper heart rate threshold and no SAEs or AEs were observed. Lastly, in our preliminary work (ESCAPE trial; STH20750), 4 acute stroke patients successfully completed a single 30-minute moderate-intensity exercise session (13/20 RPE) and there were no AEs or SAEs. Importantly, none of the aforementioned studies reported follow-up safety outcomes. **We can confirm that there have been no SAEs or AEs related to aerobic exercise in the 3 months following our investigation.** In summary, there have been approximately 276 reported bouts of aerobic exercise conducted in the acute phase of stroke, ranging from 6 to 30 minutes in duration and from moderate to vigorous intensity. No SAEs have been reported, whereas the AE rate ranged from 0-14.7% (mean 12%). The higher frequency of AEs appears to be related to high exercise volume and the mode of exercise training (e.g. treadmill exercise twice per day for 5 days).

In our proposed aerobic exercise training intervention, participants will exercise at a moderate intensity (40-59% HRR; 12-13/20 RPE). Moderate-intensity aerobic exercise elicits a transient increase in cerebral perfusion and neurotrophin concentration (39,59) which may contribute to improved recovery after stroke (24–26). Exercise duration will gradually increase from 10 minutes in the first session (day 1) to 30 minutes in the fifth session (day 5) (5-minute increment per day). Heart rate (HR) will be monitored continuously during exercise to ensure that moderate intensity is not exceeded. Heart rate reserve – the difference between resting HR and HRmax – represents the capacity for the HR to increase under stress. Measurement of HRmax is not appropriate due to the required vigorous exercise intensity. Instead, age-predicted HRmax will be calculated using the Inbar equation which estimates HRmax with greater accuracy than the commonly used formula of 220-age (66).

Inbar equation: $205.8 - (0.685 \times \text{age})$.

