8.5.2. Risks of aerobic exercise training

Previous studies have shown that aerobic exercise is safe for people to do in the first week after stroke. So far, 276 aerobic exercise bouts have been completed in the first week after stroke. 237 sessions (86%) involved walking, 32 sessions (12%) involved seated cycling or stepping, and 7 sessions (3%) involved sit-to-stand exercise. From these studies, we estimate that the risk of:

- Cardiovascular, neurological, or musculoskeletal complications is less than 1% (no adverse events have happened so far).
- Lower-limb pain is less than 2% (adverse events only happened in treadmill exercise).

- Getting a blister or superficial wound on the foot is 1.1% (adverse events only happened in treadmill exercise. Cycling places less pressure on the feet than walking).
- Dizziness is less than 7% (adverse events only happened in treadmill exercise which is possibly related to an upright head position. Cycling will be completed in bed with a reclined backrest).

[figure not shown]

Figure 4. Pie charts displaying the risk of adverse events related to aerobic exercise.

9. Investigations

Table 3. Schedule of investigations and outcome measures. Note: orange ticks indicate standard care.

	Study period																		
	Enrolment	Allocation	Post-allocation																
Post-stroke timeline	24-72 h (study starts)				≥48 h; 5-day intervention								+1 day	Follow-up					
	24-72 h (study starts)				≥48 h; 5-day intervention									+2 weeks	+3 months (study ends)				
Study timeline	t_{-1}	t_0		t_1		t_2		t_3		t_4		t_5		t_6		t_7		t_8	
	Group →	C	I	C	I	C	I	C	I	C	I	C	I	C	I	C	I	C	I
Eligibility screen	✓																		
Informed consent			✓	✓															
Age, sex, ethnicity			✓	✓															
Time since stroke (hours)	✓																		
Stroke severity (NIHSS)			✓	✓											✓	✓		✓	✓
Cardiovascular risk profile			✓	✓															
Group allocation			✓	✓															
Thigh muscle morphology (ultrasound)			✓	✓											✓	✓		✓	✓
Thigh accelerometer fitted			✓	✓															
Inpatient physical activity levels (thigh accelerometer)					✓	✓	✓	✓	✓	✓	✓	✓	✓	✓					

	Study period																	
	Enrolment	Allocation	Post-allocation															
Post-stroke timeline	24-72 h (study starts)				≥48 h; 5-day intervention								+1 day	Follow-up				
	+2 weeks			+3 months (study ends)														
Study timeline	t_{-1}	t_0		t_1	t_2		t_3	t_4		t_5	t_6		t_7	t_8				
	Group →	C	I	C	I	C	I	C	I	C	I	C	I	C	I	C	I	

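### Sections 8.3 and 8.5.2 count at least 14 exercise tests done after day 7 as first-week bouts, so the 276-bout total and the dizziness risk of less than 7% are wrong for the period stated

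*Protocol*

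**What the plan says.** Section 8.3 of the protocol reviews earlier work on exercise soon after stroke and concludes that "there have been approximately 276 reported bouts of aerobic exercise conducted in the acute phase of stroke". It gives a mean adverse event (AE) rate of 12% over these bouts.

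Section 8.5.2, the lay account of risks, repeats the total without the qualifier: "So far, 276 aerobic exercise bouts have been completed in the first week after stroke". It splits the total by mode: "237 sessions (86%) involved walking, 32 sessions (12%) involved seated cycling or stepping, and 7 sessions (3%) involved sit-to-stand exercise". It then puts the risk of dizziness at less than 7%.

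One of the contributing studies, a graded exercise test study, is described in section 8.3 as covering acute and subacute patients ("n=28, days post-stroke: median = 9; range = 5-11"). The same sentence takes acute to mean 1 to 7 days and says that the study did not report how many patients were in that phase.

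**The concern.** The protocol's acute phase and the lay summary's first week are the same period, days 1 to 7. A study with a median of day 9 cannot lie wholly inside it. If all 28 of its tests are in the 276, the total is mislabelled. These tests produced no AEs, so counting them adds to the denominator and nothing to the numerator, and the first-week rates come out too low.

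Two things are at stake: a factual statement to patients about how much first-week evidence exists, and how much of it concerns seated exercise, the mode closest to this trial's in-bed cycling.

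**Working it through.** **Inputs, all from the protocol**

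| Source | Bouts | AEs | Timing given |
|---|---|---|---|
| Treadmill study (4.3, 8.3) | 224 | 33, of which 19 dizziness | start at 41.5 ± 14 h, 5-day programme |
| Six-minute tests (8.3) | 14 walk, 1 not completed; 7 sit-to-stand | 0 | median 4 days, no range |
| Graded exercise tests (8.3) | 28 | 0 | median 9 days, range 5–11 |
| Team's preliminary work (8.3) | 4 | 0 | acute |

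The treadmill dizziness count is stated as "Dizziness was the most frequent AE, occurring in 8.5% (19/224) of all exercise sessions".

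**Step 1: reproduce the stated figures**

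- Walking: 224 + (14 − 1) = 237, as stated.
- Seated cycling or stepping: 28 + 4 = 32, as stated.
- Sit-to-stand: 7, as stated.
- Total: 237 + 32 + 7 = 276, as stated.
- Dizziness: 19/276 = 6.88%, consistent with less than 7%.
- All AEs: 33/276 = 11.96%, consistent with 12%.

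Every figure matches, and the 32 seated sessions can be reached only with all 28 graded tests included.

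**Step 2: how many of the 28 can be first-week?**

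Let k be the number of graded tests within days 1 to 7. With n = 28, the median is the mean of the 14th and 15th ordered values. A median of 9 makes the 15th value at least 9, so the 15th to 28th all lie after day 7. Hence k ≤ 14. The upper end is extreme: it needs the 14th value at 7 and the 15th to 28th all at 11. The minimum of day 5 gives k ≥ 1.

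**Step 3: recompute**

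The bouts other than the graded tests number 276 − 28 = 248, so the first-week denominator is 248 + k.

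| | As stated (k = 28) | k = 14 | k = 1 |
|---|---|---|---|
| Denominator | 276 | 262 | 249 |
| Dizziness, 19/(248 + k) | 6.88% | 7.25% | 7.63% |
| All AEs, 33/(248 + k) | 11.96% | 12.6% | 13.3% |
| Seated cycling or stepping, 4 + k | 32 | 18 | 5 |

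**Step 4: could dizziness still be below 7%?**

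That needs a denominator above 19/0.07 = 271.4, so at least 272, and k ≥ 272 − 248 = 24. Step 2 caps k at 14. The statement fails for every feasible split.

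**The case against.** The strongest reply is that little is lost. The sums are correct as sums; the fault is the label on the period. Dizziness moves by only 0.37 to 0.75 percentage points (7.25 − 6.88; 7.63 − 6.88). The protocol prints the undiluted 8.5% for the treadmill study in sections 4.3 and 8.3. Section 8.3 admits that the acute share of the 28 is unknown and calls the total approximate. Patients are told that dizziness arose only in treadmill exercise and that they will cycle reclined in bed. The success criteria in section 6.3 use AE counts, so no threshold depends on these rates. All of this stands and limits the size of the point. It does not make the first-week sentence or the dizziness figure true.

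A reader might infer more than the documents support:

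- **That 248 is the verified first-week denominator, giving 19/248 = 7.66%.** At least one graded test was on day 5, so 248 is below the feasible range. The other bouts are not fully verified either. The six-minute tests have a median but no range, and the treadmill timing leaves room for a late starter's last sessions to fall near or past day 7. Also, 20 patients exercising twice daily for 5 days gives 200 sessions, not the 224 printed; I have used 224 as stated.
- **That all the lay risk figures are wrong.** Event counts for lower-limb pain (less than 2%) and blisters (1.1%) are not given. Assuming 3 blister events, the rate goes from 1.09% to between 1.15% and 1.20%. Assuming 5 pain events, it becomes 1.91% to 2.01%; with 4 it stays below 2%. Complications have no events, so the observed rate stays at zero.
- **That the risk category in section 8.4.1 is undermined.** That section relies on the absence of serious AEs and on risk procedures, not on these percentages, and already cites uncertainty in choosing type B.
- **That patients are told the 12% overall rate.** It appears in section 8.3, not in the lay text.

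**Conclusion.** The point holds as a mislabelled period with a wrong figure resting on it. At least 14 of the 276 bouts were after day 7. For the first week, dizziness is 7.3% to 7.6% and not below 7%, the overall AE rate is 12.6% to 13.3%, and seated cycling or stepping sessions number 5 to 18. The stated denominator is 5% to 11% too large (276/262 = 1.053; 276/249 = 1.108).

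The ranges rest on two assumptions: that the median and range in section 8.3 are correct, and that the treadmill, six-minute and preliminary bouts all count as first-week, as the protocol treats them. A single corrected value cannot be given, because the acute share of the 28 tests is unknown. The effect on the rates is modest. The effect on the evidence for seated exercise is larger: "32 sessions (12%) involved seated cycling or stepping" overstates the first-week count by at least 14 sessions (32 − 18) and by as many as 27 (32 − 5).

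**What to change.** Amend sections 8.3 and 8.5.2 in one of two ways.

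1. Relabel the 276 as bouts within about 11 days of stroke. The 6.9%, the 12% and the 32 seated sessions then stand, with the longer period stated next to them.
2. Keep the first-week wording, take the 28 graded tests out of the total and report them separately as done on days 5 to 11 with the acute share unknown. For any first-week claim, give dizziness as about 7% to 8% (7.3% to 7.6%), the overall AE rate as about 13%, and seated cycling or stepping sessions as 5 to 18. The mode percentages then need restating too: seated sessions are 5/249 = 2.0% to 18/262 = 6.9% of the total, not 12%.

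Figure 4 and the participant information were not available to check; change them in the same way if they repeat these figures.

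The cost is a wording amendment and slightly less favourable stated risks. Design, sample size and success criteria are unaffected.

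### The dizziness risk to be told to patients stays below 7% only by counting bouts done after the first week, and none of the risks is labelled as per session

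*Protocol*

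**What the plan says.** Section 8.5 holds the risks and benefits to be communicated to patients. Section 8.5.2 gives the evidence base, "So far, 276 aerobic exercise bouts have been completed in the first week after stroke", and splits it by type of exercise: "237 sessions (86%) involved walking, 32 sessions (12%) involved seated cycling or stepping, and 7 sessions (3%) involved sit-to-stand exercise". It then lists estimated risks:

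- "Dizziness is less than 7" per cent.
- A blister or superficial foot wound: 1.1%.
- Lower-limb pain: below 2%.
- For cardiovascular, neurological or musculoskeletal events, the risk of "complications is less than 1% (no adverse events have happened so far").

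It adds that dizziness, pain and blisters were seen only with treadmill exercise. The text attaches no unit (per session or per participant) to any of these risks.

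Section 8.3 describes the source studies. It puts the same total of about 276 bouts in the acute phase, which it defines as days 1 to 7, and gives a mean adverse event rate of 12%. For the treadmill training study it reports "occasional dizziness (8.5%; 19/224 sessions"). For the graded exercise test study (n=28) it reports "days post-stroke: median = 9; range = 5-11", and it notes that the share of acute patients was not specified.

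Section 12.3.3 plans five exercise sessions per intervention participant, fewer if the patient is discharged early.

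**The concern.** Two things do not fit. First, all 276 bouts are placed in the first week, yet a study with a median of day 9 appears to be among them. If so, the denominator is too large for the statement it supports, and 6.9% leaves almost no room under a 7% bound. Second, the percentages are proportions of bouts. A patient who is told the risk of dizziness will probably take it as the risk from joining the study, and joining means up to five sessions.

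These numbers are intended for consent. A stated upper bound that the document's own figures exceed, with an unstated unit, should not go to patients, even if the error is small.

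**Working it through.** **Rebuilding the denominator**

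Inputs, all from section 8.3 (the 224 sessions are also in 4.3):

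- Treadmill training study: 224 sessions.
- Six-minute test study: 14 walk tests, one not completed, leaving 13; and 7 sit-to-stand tests.
- Graded exercise test study: 28 tests.
- The sponsor's preliminary study: 4 sessions.

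Walking: 224 + 13 = 237. Cycling or stepping: 28 + 4 = 32. Sit-to-stand: 7. Total: 237 + 32 + 7 = 276. This matches the split in 8.5.2 exactly, so all 28 graded tests are in the total.

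**Reproducing the stated figures**

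- Dizziness: 19/276 = 6.88%, stated as below 7%.
- All adverse events ("33 AEs in 224 exercise sessions", section 4.3): 33/276 = 11.96%, stated as a mean of 12%.
- Blister or wound: 3/276 = 1.09%, stated as 1.1%. The count of 3 is inferred from the percentage.

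The denominator is therefore bouts. No whole number of people gives 1.1%: one person in 73 (20 + 21 + 28 + 4) is already 1.37%.

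**Bouts after day 7**

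With n = 28, the median is the mean of the 14th and 15th ordered values. A median of 9 makes the 15th to 28th values at least 9, so at least 14 tests were after day 7. A minimum of 5 puts at least one test within day 7, so at most 27 were after it. The first-week total is thus 276 − 14 = 262 at most and, removing only these tests, 276 − 27 = 249 at least. The treadmill sessions are all taken as first-week: that study recruited at 41.5 ± 14 hours and ran for five days (section 4.3).

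| | 276 bouts | 262 bouts | 249 bouts |
|---|---|---|---|
| Dizziness, 19 events | 6.88% | 7.25% | 7.63% |
| All adverse events, 33 | 11.96% | 12.60% | 13.25% |
| Blister or wound, 3 | 1.09% | 1.15% | 1.20% |

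Removing five bouts is enough to pass 7%: 19/272 = 6.99%, 19/271 = 7.01%. In the treadmill study alone, 19/224 = 8.48%.

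**From session to participant**

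For a per-session risk p and five sessions:

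- Events fully clustered in the same patients: p, or 7.3% to 7.6%.
- Sessions independent: 1 − (1 − p)^5, or 31.4% (19/262) to 32.8% (19/249).
- No patient affected twice: 5p, or 36.3% to 38.2%.

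**Zero complications**

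The one-sided 95% upper limit for 0 events in n sessions is 1 − 0.05^(1/n). This is 1.08% for n = 276, 1.14% for n = 262 and 1.20% for n = 249.

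**The case against.** The strongest reply is that 19/276 is correctly computed, and that the fault lies in three words about timing that move one symptom from 6.9% to at most 7.6%. That is fair as to size. It does not remove the contradiction between 8.5.2 and the timing given in 8.3, nor the fact that the first-week figure lies above the stated bound.

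It can also be said that the unit is inferable, because the paragraph counts bouts and sessions before giving the risks. A statistician would infer it; a patient may not. Figure 4 is not reproduced here and the information sheets are separate documents, so either may already label the unit.

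Several stronger conclusions are tempting and are not supported:

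- *That all the stated risks are wrong.* Only dizziness is shown to cross its bound. The blister figure barely moves, and no count is given for lower-limb pain, so it cannot be recomputed.
- *That about a third of participants will become dizzy.* This needs independent sessions, which nothing in the protocol supports or refutes. It also carries treadmill dizziness over to semi-recumbent cycling. The protocol reports dizziness only on the treadmill and gives a postural reason.
- *That the statement "More than half of participants experienced at least 1 adverse event (AE) during exercise" in section 4.3 applies here.* That study used twice-daily 30-minute treadmill sessions; this one plans one session a day, starting at 10 minutes.
- *That the figure below 1% for complications is false.* It holds as a point estimate, and its basis of no events is disclosed. The data simply do not exclude slightly more than 1%.
- *That all 28 graded tests should be removed.* The range shows that at least one was within day 7.
- *That the safety progression rule is affected.* Section 6.3 counts related events and uses no rate from 8.5.2.

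**Conclusion.** The point holds in a limited form. The statement that all 276 bouts fell in the first week is contradicted by section 8.3: 14 to 27 of them did not. On a first-week basis dizziness is 7.3% to 7.6% per bout, against a stated bound of 7%. This follows from the reported median and range, and assumes only that all treadmill sessions, and so all 19 events, were within the first week. If any six-minute tests were also after day 7, the percentage would rise a little further.

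Separately, the risks are per bout without a label, while participants are offered five sessions. The chance of at least one event over the programme may be higher than the quoted figure. How much higher cannot be settled from the document: for dizziness it runs from about 7% under full clustering to 31–33% under independence, and that only if treadmill rates carried over to in-bed cycling. The error is modest, but it is in numbers meant for consent and is easily corrected.

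**What to change.** 1. In 8.3, 8.5.2 and Figure 4, either stop describing the 276 bouts as first-week or acute-phase, or restate the denominator as at most 262 and recompute what depends on it: dizziness 7.3% to 7.6%, mean adverse event rate 12.6% to 13.3%, blister or wound about 1.2%. Change 8.3 and 8.5.2 together so that they agree.
2. Label every risk as per exercise session. State that each intervention participant is offered up to five sessions, so the chance of at least one event over the programme may be higher.
3. If a per-participant figure is added, give it as a range with its assumption (about 7% if events cluster fully in the same patients, about 31–33% if sessions are independent), and note that dizziness was seen only in treadmill exercise.
4. For complications, say that none has been seen so far in N sessions instead of giving a firm bound of 1%. If a limit is wanted, the one-sided 95% upper limit is about 1.1% per session.
5. Check the information sheets for the same figures.

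The cost is a wording change to the protocol and, where they repeat the figures, the patient documents. The stated risks become slightly less favourable. Design, sample size and procedures are unchanged.

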
The day after completing the first exercise bout, participants will undertake a single aerobic exercise session per day for 4 days (5 exercise sessions in total). If patients are discharged earlier, study participation will terminate on the day of discharge. The workload that elicited an RPE of 13 at the start of the conditioning phase in the first aerobic exercise session will be used to guide the initial workload for the conditioning phase in subsequent sessions.

Number of repetitions (rpm multiplied by minutes) completed during the warm-up,

conditioning phase and cool-down will be included within therapy dose calculations. Verbal communication provided by the operator will be standardised (detailed in Table 6, Appendix).

Through consultations with stroke survivors and healthcare practitioners we acknowledge the need for a flexible exercise protocol. It was expressed to us that patients' level of fatigue and physical function may fluctuate throughout the duration of hospital stay depending on various intrinsic and extrinsic factors. Thus, the workload used for each exercise session will be a collaborative choice made between the researcher and the participant.

[figure not shown]

Figure 5. Schematic diagram of 5-day exercise protocol.

Note: Blue = passive cycling (no exertion) = 5 minutes; brown = warm up/cool down; pink = active cycling (moderate intensity). Active cycling duration = 5 minutes per bout. Passive recovery intervals = 1 minute (blue).

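### The patient risk summary in 8.5.2 gives per-session rates as bare risks, although each participant is offered five sessions

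*Protocol*

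**What the plan says.** Section 8.5 is the lay summary of what patients are to be told. Section 8.5.2 first gives the evidence base: "So far, 276 aerobic exercise bouts have been completed in the first week after stroke". It then splits these by mode: "237 sessions (86%) involved walking, 32 sessions (12%) involved seated cycling or stepping, and 7 sessions (3%) involved sit-to-stand exercise". The list of risks opens with "From these studies, we estimate that the risk of" and gives bare percentages, including "Dizziness is less than 7% (adverse events only happened in treadmill exercise". The lines for pain, blisters and dizziness each say that the events arose only in treadmill exercise. The dizziness line adds that cycling will be done in bed with a reclined backrest.

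Section 4.3 describes the treadmill study that supplies most of the bouts: 20 participants and 224 sessions. It reports "Dizziness was the most frequent AE, occurring in 8.5% (19/224) of all exercise sessions", a rate of 33 adverse events in 224 sessions (14.7%), and "More than half of participants experienced at least 1 adverse event (AE) during exercise". Section 12.3.3 sets the course for this trial: after the first session, "participants will undertake a single aerobic exercise session per day for 4 days (5 exercise sessions in total").

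**The concern.** A patient deciding whether to join wants to know the chance that something happens to them if they take part. A rate per session answers a different question when taking part means up to five sessions. The two units give the same number only if the same people have the event every time.

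The protocol's own source shows how far apart they can be: 14.7 adverse events per 100 sessions, yet more than half of the people affected. The authors had that person-level result, but the lay summary does not pass it on. At stake is the accuracy of the risk information behind consent. No endpoint, sample size or progression rule depends on these percentages.

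**Working it through.** **Reproducing the plan's figures**

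- Bouts by mode (8.5.2): 237 + 32 + 7 = 276.
- Bouts by source (4.3 and 8.3): 224 treadmill sessions + 13 completed walk tests + 7 sit-to-stand tests + 28 graded tests + 4 from the preliminary study = 276.
- Share from the 20 treadmill participants: 224/276 = 81%.
- Dizziness: 19/276 = 6.88%, which is the stated ceiling of 7%.
- Any adverse event: 33/276 = 11.96%, which is the mean of 12% in 8.3.
- Blisters: 1.1% would match 3/276 = 1.09%. The count of 3 is inferred, as the protocol does not give it. The pain count is not given either.

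The dizziness figure is therefore a rate per bout.

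**From one session to five**

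Let p be the chance per session and n = 5.

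- Independent sessions: 1 − (1 − p)^5. With p = 19/276, 1 − 0.9312^5 = 30.0%.
- Complete clustering, with the same people affected every time: the chance stays at p = 6.9%.
- With p = 19/224, the treadmill rate alone, the limits are 35.8% and 8.5%.

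The number of people who had dizziness is not reported, so the data alone do not narrow this further.

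**Calibration to the person-level result in 4.3**

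Use a beta-binomial model with within-person correlation ρ, where a = p(1 − ρ)/ρ and b = (1 − p)(1 − ρ)/ρ. Then P(at least one in n) = 1 − B(a, b + n)/B(a, b). The treadmill participants averaged 224/20 = 11.2 sessions. With p = 33/224, independence would predict that 1 − (1 − 33/224)^11.2 = 83% had an adverse event. Section 4.3 says only that more than half did, so ρ is solved over a range of shares:

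| Assumed share with any adverse event | ρ | Five-session dizziness at 19/276 | at 19/224 |
|---|---|---|---|
| 50.1% | 0.303 | 19.3% | 23.3% |
| 60% | 0.186 | 22.6% | 27.2% |
| 70% | 0.093 | 25.8% | 31.0% |
| 80% | 0.020 | 29.0% | 34.6% |

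At the plan's own rate this gives about 19-29%, roughly three to four times 6.9%. Two assumptions are needed. The clustering of all adverse events must carry over to dizziness. The 33 events must also be treated as 33 affected sessions, although one session could hold more than one event.

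**Pain and blisters**

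If the stated percentages are also per bout, the same limits apply. Blisters run from 1.1% to 1 − 0.989^5 = 5.4%. For pain, the ceiling of 2% becomes at most 1 − 0.98^5 = 9.6%.

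**The case against.** The strongest reply is that the percentages do not describe this intervention. Every dizziness, pain and blister event came from treadmill exercise, mostly twice-daily 30-minute walking, and 8.5.2 says so on each line. The trial uses one semi-recumbent cycling session a day, and none of these events occurred in the 32 cycling or stepping bouts. Early discharge also ends participation, so some people will do fewer than five sessions. All of this stands, and it means that no five-session figure here is a forecast for in-bed cycling. But it bears on whether the rate transfers, not on its unit. Zero events in 32 bouts is also weak reassurance, with a one-sided 95% upper limit of 1 − 0.05^(1/32) = 8.9% per bout.

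A second reply is that the lead-in counts bouts and sessions, so the unit can be worked out. A statistician can do that; a patient reading the risk lines is not told. Figure 4 and the participant information sheet are not available, so their labels cannot be checked.

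Three stronger readings are tempting, and the protocol does not support them:

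- A reader might infer that the data fix the five-session dizziness risk at about 15-30%. They do not. The upper end assumes independent sessions, and the lower end needs a correlation of about 0.49 that no input supplies. The exhaustion data cannot settle it either. Section 8.3 does not class exhaustion as an adverse event and reports "24 out of 224 (10.7%) exercise sessions ended early as a result of exhaustion (9/20 participants"), while 4.3 gives 28 sessions and says that the number of participants was not reported.
- A reader might infer that the plan treats bouts as independent. It states no such assumption. Events divided by bouts is a valid rate per bout whatever the clustering, and no interval is attached to these lines.
- A reader might infer that 8.5.2 contradicts 4.3. It does not: 14.7% of sessions and more than half of participants are compatible, and 8.5.2 gives no overall adverse-event risk.

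**Conclusion.** The point holds as an error of unit in patient-facing text. The dizziness figure is demonstrably per bout. The pain and blister figures very probably are too, though their counts are not given. Read as the risk of taking part, they are too low unless events recur in the same people at every session. At the plan's own dizziness rate, the five-session chance is bounded by 6.9% and 30.0%. About 19-29% is a reasonable working range if the clustering implied by 4.3 applies to dizziness. These sizes describe five sessions at the pooled, treadmill-dominated rate. The matter deserves correction because it informs consent, but it does not threaten the validity of the trial.

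**What to change.** In 8.5.2 and the patient-facing risk text drawn from it:

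1. Label each percentage 'per exercise session'.
2. Add the person-level result from 4.3: more than half of the 20 people in the treadmill study had at least one adverse event.
3. If a five-session figure is given, state it as a range that depends on assumptions, about 7-30% for dizziness, and say that it rests on treadmill data.
4. Keep the caveat that none of these events occurred in cycling.

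No new data or design change is needed. The cost is that the stated risks look less favourable, and that the new wording may need an amendment if the text is already approved.
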